### 7.3.3 Safety Analyses

The safety profile will be evaluated using the Safety analysis population and evaluated using data collected throughout follow-up. Analyses will be primarily descriptive reporting the number and percentage of adverse events along with categorizations of seriousness, severity, frequency (within a subject), and perceived relatedness to the

CONFIDENTIAL

This material is the property of the University of Minnesota. Do not disclose or use except as authorized in writing by the study sponsor

intervention. In addition, incidence of disordered eating behaviors will be evaluated between groups and monitored by the data and safety monitoring board (DSMB) throughout the trial.

#### **7.4 Missing Data**

Despite best efforts, it is possible that some data will be missing, which could limit the interpretation and generalizability of results. If the missing data is missing completely at random, the consequence will merely be lost precision. Based upon attrition rates in our previous trials, we anticipate that no more than 20% of the participants will be lost to follow-up. Taking this into account, the planned enrollment of 130 is inflated to account for potential drop out. As such, in the ‘worst case’ situation of observing missing data as high as 20%, we will still have >85% and >95% power to detect a 4% and 5%, respectively, control-subtracted percent change in BMI from randomization to 52 weeks (primary endpoint). If the data are missing at random, conditioned on measured covariates, then supplementary analyses adjusting for these covariates will produce unbiased results. For potential missing data mechanisms beyond measured covariates, we will examine the extent to which results may be affected. Imputation techniques will be considered for missing data issues (e.g., multiple imputation). Secondary endpoints will be handled similarly. We do not expect to observe differential attrition by treatment arm based on results of adult financial incentives trials demonstrating nearly identical study completion rates among the control and treatment groups. But, it is possible we may observe differential attrition. Sensitivity analyses will include differential imputed values to examine the degree of robustness of the results. We will also collect data on why participants decide to discontinue, enabling us to examine differences between study arms and in participant characteristics between completers and dropouts.

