## Study Summary

Title	Enhancing Weight Loss with Financial Incentives in Teens
Phase	N/A
Methodology	Randomized, controlled clinical trial
Study Duration	5 Years
Study Center	University of Minnesota Center for Pediatric Obesity Medicine in collaboration with the Minnesota Pediatric Obesity Consortium (MN-POC)
Objectives & Hypotheses	
Primary Objective: Evaluate the effect of meal replacement therapy plus financial incentives on weight loss, cardiometabolic risk factors, vascular health, and behavior change among adolescents with severe obesity. We hypothesize that the use of meal replacement therapy with financial incentives (vs. no financial incentives) will lead to greater percent reduction in BMI (primary endpoint) as well as reduce body fat, blood pressure, triglycerides/HDL ratio, inflammation, oxidative stress, arterial stiffness, and improve heart rate variability at 26 and 52 weeks.
 
Secondary Objectives: Identify weight loss thresholds associated with significant improvements in cardiometabolic risk factors and vascular health in adolescents with severe obesity. We hypothesize that a minimum weight loss threshold exists, that when exceeded, will be associated with meaningful improvements in multiple cardiometabolic risk factors and parameters of vascular health.

Number of Participants	130
Diagnosis and Main Inclusion Criteria	
Diagnosis: Severe obesity
 
Main Inclusion Criteria:
 
 
• BMI <math>\geq</math>1.2 times the 95th percentile (based on sex and age) or BMI <math>\geq</math>35 kg/m^2
 
• Age 13-17 years
 

Study Intervention	All participants will engage in 52 weeks of meal replacement therapy. Participants will be randomly assigned to receive financial incentives for weight loss or no financial incentives.
Statistical Methodology	The primary analysis will be conducted using the intent-to-treat population to compare the mean BMI percent change from randomization to 52 weeks (additional analyses will use the 26-week time-point as secondary) of follow-up between the financial incentives and no financial incentives groups, adjusted for BMI at randomization and insurance status (randomization stratification factor) for added precision. Confidence intervals (CIs) and P-values will be based on robust variance estimation. Statistical significance will be considered as p<0.05.

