This study will afford a unique opportunity to address another key unanswered question related to the treatment of pediatric severe obesity: how much weight loss is necessary to elicit clinically-meaningful improvements in cardiometabolic risk factors and vascular health? It will be critically important for pediatricians to have evidence-based weight loss targets for their patients with severe obesity since it will better inform the type and intensity of the treatments selected in clinical practice. Although evidence-based benchmarks have been established for adults, no such thresholds have been identified for youth with severe obesity. Therefore, we plan to conduct a 12-month randomized, controlled clinical trial to evaluate the effects of meal replacement therapy plus financial incentives on weight loss and cardiometabolic/vascular outcomes among 142 adolescents (ages 13-17 years old) with severe obesity and to identify thresholds of weight loss required to achieve clinically-meaningful cardiometabolic/vascular improvements in this patient population. Importantly, we will be able to characterize the degree of normalization of risk factors and vascular outcomes according to amount of weight loss and compare post-intervention values to a database of youth with normal weight, overweight, and obesity in the same age-range tested in the same laboratory using identical methods.

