## 7.2 Sample Size Determination

Based on results of adult clinical trials of financial incentives for weight loss, we anticipate a control-subtracted treatment effect (BMI reduction, our primary endpoint) of 5% at 52 weeks. We estimate having a dropout rate of no more than 20% (our previous clinical trial experience with this population has been 10-15%). We do not expect to observe differential attrition by treatment arm based on results of adult financial incentives trials demonstrating nearly identical study completion rates among the control and treatment groups. Using BMI variability estimates from a previous trial using meal replacements over 12 months suggesting a standard deviation of approximately 8.8 and using a conservative correlation between baseline and follow-up scores of 0.6, we present in Table 2 the power associated with a clinically-meaningful control-subtracted BMI reduction of 5% based on an overall sample size of 130 (60 in each treatment arm) and a range of degrees of attrition (including rows reflecting scenarios of higher than expected levels).

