**Table 2. Conservative Estimates of Power for a Range of Potential Treatment Effects at 52 Weeks**

Difference in BMI Percent Change	5%
Two-sided Unadjusted	97.18%
Two-sided with 10% attrition	95.67%
Two-sided with 15% attrition	94.5%
Two-sided with 20% attrition	93.25%

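### Section 7.4 overstates power at 20% missing data: a 4% effect has about 79–82% power, not more than 85%, and the 5% figure contradicts Table 2

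*Combined protocol and SAP*

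**What the plan says.** Section 7.4 (Missing Data) takes an enrolment of 130, treats 20% missing data as the worst case, and states that "we will still have >85% and >95% power to detect a 4% and 5%, respectively, control-subtracted percent change in BMI" from randomization to 52 weeks, the primary endpoint.

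Section 7.2 (Sample Size Determination) sets out the inputs. The design effect is given as "we anticipate a control-subtracted treatment effect (BMI reduction, our primary endpoint) of 5% at 52 weeks". The variability comes from a previous 12-month meal replacement trial "suggesting a standard deviation of approximately 8.8", and the calculation is made "using a conservative correlation between baseline and follow-up scores of 0.6". Power is then presented "based on an overall sample size of 130 (60 in each treatment arm").

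Table 2 has a single effect column, 5%. It gives 97.18% without attrition, 95.67% at 10%, 94.5% at 15%, and 93.25% in the row "Two-sided with 20% attrition". It has no 4% column.

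Section 5.1 specifies 1:1 randomization. Section 7.3.1 specifies that the primary comparison adjusts for BMI at randomization and insurance status. The Introduction still describes a trial in "142 adolescents (ages 13-17 years old").

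**The concern.** Two current sections give different power for the same scenario: the same endpoint, time point, 5% difference and 20% loss. One says 93.25% and the other says more than 95%.

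The 4% figure is harder for a reader to catch, because it appears only in Section 7.4 and Table 2 offers nothing to check it against. It is not a side value either. Section 1.2 reports 4% BMI reduction as the preliminary threshold for risk-factor improvement, and Section 7.3.2 uses 4% as its worked example of clinical meaningfulness. If the 4% power is overstated, the plan gives too reassuring an account of what the trial can detect below its design effect, under the attrition that it calls its worst case.

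The base is also unclear. At 1:1, 130 participants are 65 per arm, and 60 per arm is 120 participants.

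**Working it through.** **Inputs**

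- Two-sided alpha 0.05: the Study Summary states "Statistical significance will be considered as p<0.05", and the row labels of Table 2 are two-sided.
- SD 8.8 and correlation 0.6 (Section 7.2). The SD is taken to be in percentage points of BMI change; the reproduction of Table 2 below supports that reading.
- Baseline-adjusted analysis (Section 7.3.1).
- 1:1 allocation (Section 5.1) and 20% loss (Section 7.4).

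**Formulas**

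- Residual SD: 8.8 × √(1 − 0.6²) = 8.8 × 0.8 = 7.04.
- Analysed per arm: m = n × (1 − loss).
- Standard error of the difference: 7.04 × √(2/m).
- Power: two-sample noncentral t with 2m − 2 degrees of freedom and noncentrality Δ/SE. The normal approximation, Φ(Δ/SE − 1.96), is shown as a check.

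**Step 1. Reproduce Table 2 (5% difference)**

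| Loss | Table 2 | 60 per arm: m, power (t) | 65 per arm: m, power (t) |
|---|---|---|---|
| 0% | 97.18% | 60, 97.1% | 65, 98.0% |
| 10% | 95.67% | 54, 95.5% | 58.5, 96.8% |
| 15% | 94.5% | 51, 94.4% | 55.25, 95.9% |
| 20% | 93.25% | 48, 93.1% | 52, 94.8% |

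With SD 7.04, Table 2 matches 60 per arm within 0.2 points in every row and does not match 65. The model is therefore in effect the plan's own, and Table 2 was built on 120 participants.

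**Step 2. Section 7.4 scenario (20% loss)**

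For 60 per arm, m = 48 and SE = 7.04 × √(2/48) = 1.437. For a 4% difference, 4/1.437 = 2.78, and Φ(2.78 − 1.96) is about 79.5%.

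For 65 per arm, m = 52 and SE = 7.04 × √(2/52) = 1.381. For a 4% difference, 4/1.381 = 2.90, and Φ(2.90 − 1.96) is about 82.6%.

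| Effect | Section 7.4 | 60 per arm: t / normal | 65 per arm: t / normal |
|---|---|---|---|
| 4% | >85% | 78.7% / 79.5% | 81.9% / 82.6% |
| 5% | >95% | 93.1% / 93.6% | 94.8% / 95.2% |

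Using 2m − 4 degrees of freedom, to allow for the covariates, changes these by no more than 0.02 points.

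**Step 3. Other readings of the inputs at 20% loss, 60 to 65 per arm**

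- Unadjusted SD 8.8: 60–64% for 4% and 79–83% for 5%.
- Change-score SD, 8.8 × √(2 × (1 − 0.6)) = 7.87: 69–74% for 4% and 87–90% for 5%.
- SD solved backwards from Table 2's 93.25%: 78.9% for 4%.

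No two-sided reading reaches 85% for 4%.

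**Step 4. What would give the stated figures**

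- 85% power for 4% needs 56 (normal) or 57 (t) analysed per arm. At 20% loss that is 2 × 56/0.8 = 140, or 2 × 57/0.8 = 142.5, so 143 enrolled.
- 142 enrolled with 20% loss leaves 56.8 per arm and gives 85.1–85.7% for 4% and 96.3–96.6% for 5%.
- 60 per arm with no loss gives 87.0–87.5% and 97.1–97.3%.
- 60 per arm with 20% loss, tested one-sided at 0.05, gives 87.3% and 96.7%.
- 65 per arm with 20% loss and correlation 0.65 gives 85.6–86.2% and 96.5–96.8%.

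None of these is the stated plan: 130 enrolled, 20% missing, two-sided, correlation 0.6.

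**The case against.** The 5% claim is not clearly wrong at the enrolment that Section 7.4 uses. With 130 at 1:1 and 20% loss, the normal approximation gives 95.2% and the t calculation 94.8%. That stands: if 65 per arm is meant, the 5% problem is the clash with Table 2 and the unreconciled base, not a material shortfall.

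The trial is designed for 5%, where power is 93–95% on either base. The 4% shortfall is about 2.5 to 6 points and changes no endpoint, analysis or enrolment. Nor does planned power exclude anything: a null result should be read from the confidence interval, which the plan will report. This limits the consequence but does not make the stated figure correct.

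The calculation counts completers only. Section 7.1 allows multiple imputation, and BMI is measured at every visit, so partial follow-up could recover some information. However, Table 2 appears to discount attrition in full, and Section 7.4 does not say that it relied on any recovery.

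Finally, 60 per arm may be the intended base. The change history records a cut to 120 and a later rise to 130 because of recruitment interest, so the figure to correct in Section 7.2 could be 130. That is a fair alternative, and it makes the Section 7.4 figures further from the truth.

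**Conclusion.** The concern holds. At 20% loss, the claim of more than 85% power for a 4% effect is false on either base: 78.7% with 60 per arm and 81.9% with 65 (79.5% and 82.6% by normal approximation). Type II error at 4% is about 18–21% by the t calculation, where Section 7.4 implies under 15%. The claim of more than 95% for a 5% effect contradicts Table 2's 93.25%; recomputed, it is 93.1% with 60 per arm and on the border with 65. The description of 130 participants as 60 per arm cannot hold under 1:1 allocation.

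These values assume SD 8.8, correlation 0.6, full baseline adjustment, a two-sided 0.05 test, equal loss in both arms and a completers-only count. The Section 7.4 figures do fit a 142-participant design, the number still in the Introduction, so they may predate the reduction in sample size. The documents do not say so, and the error does not depend on it.

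**What to change.** Settle the per-arm base in Section 7.2, then make Section 7.2, Table 2 and Section 7.4 agree.

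If 130 at 1:1 is the base, replace 60 with 65 per arm in Section 7.2 and recompute Table 2 with a 4% column:

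| Loss | Analysed per arm | 5% | 4% |
|---|---|---|---|
| 0% | 65 | 98.0% | 89.5% |
| 10% | 58.5 | 96.8% | 86.2% |
| 15% | 55.25 | 95.9% | 84.1% |
| 20% | 52 | 94.8% | 81.9% |

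In Section 7.4, state about 82% for 4% and about 95% for 5%.

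If 60 per arm is meant as the powered base, correct the total in Section 7.2 to 120, leave the 5% column of Table 2 as it is, add a 4% column (87.0 / 83.3 / 81.1 / 78.7%), and state about 79% and 93% in Section 7.4.

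In either case, say that the figures count completers only and reconcile the 142 in the Introduction with the current enrolment. The cost is some wording and one table. Enrolment and analysis do not change; the stated power for a 4% effect becomes less favourable.

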### **8 Safety and Adverse Events**

#### **8.1 Potential Risks**

As with any research study, there may be unforeseen risks. A trained interdisciplinary research staff comprised of physicians, scientists, nurses, and coordinators carefully guard against all potential risks.

##### **8.1.1 Dual-energy X-ray Absorptiometry (iDXA) Scan**

The iDXA is painless and involves exposure to a very low dose of radiation. As part of this study, participants will undergo a total of three iDXA scans.

##### **8.1.2 Blood Sampling**

There is minimal risk of bruising and infection associated with the blood draw.

##### **8.1.3 Questionnaires**

There are no risks associated with the questionnaires to be used in the study. Participants may refuse to answer any questions or stop participating at any time.

#### **8.2 Definitions**

##### **8.2.1 Adverse Event**

An **adverse event** (AE) is any symptom, sign, illness or experience that develops or worsens in severity during the course of the study. Inter-current illnesses or injuries should be regarded as adverse events. Abnormal results of diagnostic procedures are considered to be adverse events if the abnormality:

CONFIDENTIAL

This material is the property of the University of Minnesota. Do not disclose or use except as authorized in writing by the study sponsor

- results in study withdrawal
- is associated with a serious adverse event
- is associated with clinical signs or symptoms
- leads to additional treatment or to further diagnostic tests
- is considered by the investigator to be of clinical significance

Adverse events relationship to the study will be based on the following scale:

- Unrelated: Clearly not related to study
- Unlikely: Unlikely to be related to study
- Possible: May be related to study
- Probable: Likely to be related to study
- Definite: Clearly related to study

### 8.2.2 Serious Adverse Event

Adverse events are classified as serious or non-serious. A **serious adverse event** is any AE that is:

- fatal
- life-threatening
- requires or prolongs hospital stay
- results in persistent or significant disability or incapacity
- a congenital anomaly or birth defect
- an important medical event

Important medical events are those that may not be immediately life threatening, but are clearly of major clinical significance. They may jeopardize the participant, and may require intervention to prevent one of the other serious outcomes noted above.

All adverse events that do not meet any of the criteria for serious should be regarded as non-serious adverse events.

### 8.2.3 Adverse Event Reporting Period

Adverse events will be followed from the initiation of any study procedures until the Week 52 visit. Serious adverse events will be followed from the initiation of any study procedures until resolution.

All serious adverse events will be followed from the initiation of any study procedures until the events are resolved, the participant is lost to follow-up, or the serious adverse event is otherwise explained. At the final visit, if there is an ongoing serious adverse event, the participant and the parent/guardian will be instructed to report any subsequent event(s) that they, or their personal physician, believe might be reasonably related to participation in this study.

### 8.2.4 Preexisting Condition

A preexisting condition is one that is present at the start of the study. A preexisting condition will only be recorded as an adverse event if the frequency, intensity, or the character of the condition worsens during the study period.

CONFIDENTIAL

This material is the property of the University of Minnesota. Do not disclose or use except as authorized in writing by the study sponsor

### **8.2.5 General Physical Examination Findings**

At screening, any clinically significant abnormality will be recorded as a preexisting condition. At the end of the study, any new clinically significant findings/abnormalities that meet the definition of an adverse event will be recorded and documented as an adverse event.

### **8.2.6 Abnormal Laboratory Values**

A clinical laboratory abnormality should be documented as an adverse event if any one of the following conditions is met:

- The laboratory abnormality is not otherwise refuted by a repeat test to confirm the abnormality
- The abnormality suggests a disease and/or organ toxicity
- The abnormality is of a degree that requires active management; e.g., change of dose, discontinuation of the drug, more frequent follow-up assessments, further diagnostic investigation, etc.

### **8.2.7 Hospitalization, Prolonged Hospitalization or Surgery**

Any adverse event that results in hospitalization or prolonged hospitalization will be documented and reported as a serious adverse event unless specifically instructed otherwise in this protocol. Any condition responsible for surgery will be documented as an adverse event if the condition meets the criteria for an adverse event.

Neither the condition, hospitalization, prolonged hospitalization, nor surgery are reported as an adverse event in the following circumstances:

- Hospitalization or prolonged hospitalization for diagnostic or elective surgical procedures for a preexisting condition. Surgery should **not** be reported as an outcome of an adverse event if the purpose of the surgery was elective or diagnostic and the outcome was uneventful.
- Hospitalization or prolonged hospitalization required to allow efficacy measurement for the study.
- Hospitalization or prolonged hospitalization for therapy of the target disease of the study, unless it is a worsening or increase in frequency of hospital admissions as judged by the clinical investigator.

## **8.3 Recording of Adverse Events**

At each contact with the participant and their parent/guardian, adverse events will be assessed by specific questioning and, as appropriate, by examination. Information on all adverse events will be recorded immediately in the source document, and also in the appropriate adverse event form. All clearly related signs, symptoms, and abnormal diagnostic procedures results will be recorded in the source document, although they should be grouped under one diagnosis.

All adverse events occurring during the study period will be recorded. The clinical course of each event should be followed until resolution, stabilization, or until it has been determined that the study treatment or participation is not the cause. Serious adverse events that are still ongoing at the end of the study period must be followed up to determine the final outcome. Any serious adverse event that occurs after the study period and is considered to be possibly related to the study treatment or study participation will be recorded and reported immediately.

CONFIDENTIAL

This material is the property of the University of Minnesota. Do not disclose or use except as authorized in writing by the study sponsor

## **8.4 Reporting of Serious Adverse Events**

### **8.4.1 IRB Notification by Investigator**

Reports of all serious adverse events (including follow-up information) will be submitted to the IRB within 10 working days if it falls under the UPIRTSO guidelines. Copies of each report and documentation of IRB notification and receipt will be kept in the Clinical Investigator's binder.

## **8.5 Stopping Rules**

In the event that a participant has a serious adverse event that is deemed study-related by the lead-investigator for medical safety, the participant will be required to immediately withdraw from the study. The overall study may be stopped at any time at the request of the DSMB, principal investigator, and/or lead-investigator for medical safety. The main adverse effect that we expect to observe is excessive weight loss during the meal replacement period. In the context of this trial, we will define excessive weight loss as 2 consecutive weeks during which  $\geq 5$  pounds are lost per week for those with a BMI  $<40$  kg/m^2 and  $\geq 7$  pounds are lost per week for those with a BMI  $\geq 40$  kg/m^2. Individuals endorsing vomiting, laxative use, and/or diuretic use for weight control at the baseline visit will be excluded. We will also monitor for the incidence of disordered eating behaviors using the EDE-Q questionnaire, which will be administered at all in-person study visits. Any participant endorsing vomiting, laxative use, and/or diuretic use for weight control (via the EDE-Q) at any time during the trial will be interviewed using the Eating Disorders Module of the Structured Clinical Interview for DSM-5. If disordered eating is present upon clinical interview, the participant will be removed from the trial and referred to an eating behavior specialist for clinical follow-up. If no eating disorder is present, the participant may continue in the trial. The DSMB will be given the authority to stop the trial if the occurrence of excessive weight loss and/or incidence of disordered eating are deemed to be at an unacceptably high level. Participants will be instructed that they may withdraw from the study at any time and for any reason.

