#### **4.3 *Early Withdrawal of Participants***

##### **4.3.1 *When and How to Withdraw Participants***

Participants may withdraw from the trial at any time. The study may also be stopped at any time by the principal investigator, medical officer, or IRB for any reason.

Participants who discontinue participation and withdraw consent/assent will not complete follow-up visits. However, participants who are not fully compliant with the protocol and/or who choose to stop the intervention altogether but do not withdraw consent will remain in the study for follow-up in order to preserve the ability to perform an ITT analysis. Upon completion of the trial or upon complete withdrawal from the trial, participants will be referred back to their primary care physician, if applicable.

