##### **4.3.2 *Data Collection and Follow-up for Withdrawn Participants***

If a participant withdraws consent to participate in the trial, attempts will be made to obtain permission to record follow-up data. Attempts to follow up will include three phone calls to the participant. A participant will be considered lost to follow-up if no response is obtained after three attempts.

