### **7 Statistical Plan**

#### **7.1 Participant Populations for Analysis**

The primary analysis will be on an intent-to-treat population where all randomized participants will be evaluated according to their treatment assignment (financial incentives vs. no financial incentives). The analysis will be conducted with multiple imputation techniques, if necessary. A secondary per protocol analysis will include participants who are without major protocol violations. Safety assessments will include all participants who receive any treatment according to the treatment they receive. Randomization will be stratified by health insurance status

CONFIDENTIAL

This material is the property of the University of Minnesota. Do not disclose or use except as authorized in writing by the study sponsor

(public/Medicaid vs. private), which is highly-quantifiable, clinically-relevant, and closely associated with family income and socioeconomic status.

- Intent-to-treat (ITT): All participants randomized according to the treatment assignment received.
- Per-Protocol (PP): All participants randomized without major protocol violations and who were compliant (at least 80%) with the treatment assignment received. Major protocol violations include: cessation of study meals.
- Safety Population: All participants who receive any amount of treatment according to the treatment they receive.

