## **9 Data Handling and Record Keeping**

### **9.1 Confidentiality**

Information about study participants will be kept confidential and managed according to the requirements of the Health Insurance Portability and Accountability Act of 1996 (HIPAA). Those regulations require a signed subject authorization informing the participant of the following:

- What protected health information (PHI) will be collected from participants in this study
- Who will have access to that information and why
- Who will use or disclose that information
- The rights of a research participant to revoke their authorization for use of their PHI.

In the event that a participant revokes authorization to collect or use PHI, the investigator, by regulation, retains the ability to use all information collected prior to the revocation of subject authorization. For participants that have revoked authorization to collect or use PHI, attempts should be made to obtain permission to collect at least vital status (i.e. that the subject is alive) at the end of their scheduled study period.

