#### **11.4 Potential Risks to Participants**

As with any research study, there may be unforeseen risks. A trained interdisciplinary research staff comprised of physicians, scientists, nurses, and study coordinators carefully guard against all potential risks.

Blood Sampling (fasting and during meal test)

There is minimal risk of bruising and infection associated with the blood draw.

Meal Replacements and Monitoring for Excessive Weight Loss and Disordered Eating Behaviors

Adverse events will be comprehensively documented at all study visits and during each monthly phone call. Participants will be instructed to contact study staff immediately if any adverse event is experienced. All participants will receive counseling regarding avoidance of unhealthy weight loss behaviors such as use of diuretics, diet pills, purging, or excessive exercise. However, this message will be delivered conscientiously so as not to provide participants with ideas they may not already have. We will serially assess multiple domains of unhealthy weight loss behaviors using the EDE-Q. The EDE-Q identifies disordered eating behaviors and unhealthy attitudes about weight such as purging, unhealthy obsession with dieting and/or body weight, prolonged fasting/starvation, use of laxatives to control weight, and excessive exercise. The EDE-Q has been validated and used extensively in the adolescent population and normative values and cut-points have been established for this age group. Participants will be asked to weigh themselves regularly, and monthly phone calls will be performed. We will use the in person visits to monitor for excessive weight loss defined as  $\geq 5$  pounds per week for those with a BMI  $< 40 \text{ kg/m}^2$  and  $\geq 7$  pounds per week for those with a BMI  $\geq 40 \text{ kg/m}^2$ . Participants reporting excessive weight loss will be given supplemental counseling regarding unhealthy weight loss behaviors and removed from the trial if excessive weight loss is noted for 2 consecutive visits.

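### Safety removals end trial participation, not only the intervention, and no follow-up rule provides for these participants' week-52 BMI (minor, cheap to fix)

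*Combined protocol and SAP*

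**What the plan says.** Three rules end participation in the trial itself.

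- Study-related serious adverse event (8.5): "the participant will be required to immediately withdraw from the study".
- Disordered eating confirmed at clinical interview (8.5): "the participant will be removed from the trial and referred to an eating behavior specialist".
- Excessive weight loss (11.4): "removed from the trial if excessive weight loss is noted for 2 consecutive visits". Section 8.5 defines excessive loss but does not itself remove anyone for it.

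Other leavers have a follow-up provision.

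- Participants who are not fully compliant, or who choose to stop the intervention without withdrawing consent, "will remain in the study for follow-up in order to preserve the ability to perform an ITT analysis" (4.3.1).
- After consent withdrawal, "attempts will be made to obtain permission to record follow-up data" (4.3.2).
- After authorization to use health information is revoked, "attempts should be made to obtain permission to collect at least vital status" (9.1).

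Section 7.1 defines the intent-to-treat population as "All participants randomized according to the treatment assignment received". Sections 7.1 and 7.4 plan multiple imputation where needed and sensitivity analyses with differential imputed values.

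**The concern.** A participant who abandons the meals is still measured at week 52, while one taken out for harm is not, although both belong to the primary analysis population. That works against the purpose 4.3.1 gives for retaining people who stop treatment. The removals may also be related to arm and outcome: incentives are paid for weight loss, and two of the three triggers concern rapid weight loss or disordered eating. Each removal turns a primary outcome that might have been measured into one that must be imputed. At stake is some bias in the treatment difference and a small loss of precision.

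**Working it through.** **Does any follow-up rule reach these participants?**

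- 4.3.1 does not. Its retained groups are people who fall short on compliance or choose to stop, and a participant removed by the investigator has done neither.
- 4.3.2 has a broad heading, but its operative sentence is conditional on consent withdrawal, and it does not name week-52 BMI.
- 9.1 concerns revoked authorization.
- 8.2.3 gives continued safety contact: "Serious adverse events will be followed from the initiation of any study procedures until resolution". That follows the event, not BMI.
- 12.3 pays participants withdrawn early only for visits already completed, which fits a reading in which visits stop.

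No sentence provides for the measurement.

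**Inputs for sizing.** From 7.2: SD 8.8, baseline correlation 0.6, target difference 5 points, attrition up to 20%. From 3.1 and 5.1: 130 participants randomized 1:1, so 65 per arm. Removal rates are not given and are assumed throughout.

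**The plan's own figures.** The residual SD is 8.8 × √(1 − 0.36) = 7.04. With 60 per arm, the number stated in 7.2, the normal approximation gives power of 97.3 / 95.8 / 94.8 / 93.6% at 0 / 10 / 15 / 20% attrition. Table 2 states 97.18 / 95.67 / 94.5 / 93.25%, so it reproduces. The follow-up gap changes none of these figures.

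**Weight trigger (11.4), read as loss between visits.** Two consecutive visits take the participant to week 17.

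- Loss needed: 5 × 17 = 85 lb (BMI below 40) or 7 × 17 = 119 lb (BMI 40 or more).
- At assumed starting weights: 85/250 = 34.0%, 85/300 = 28.3%, 119/350 = 34.0%, 119/400 = 29.8%.
- Assumed week-17 loss: mean 10% with incentives and 6% in control, SD 7. Section 1 cites a 6% BMI reduction at 4 months with meal replacements.
- Expected removals, 65 × [1 − Φ((cut-off − mean)/7)]: 0.02 / 0.29 / 0.02 / 0.16 with incentives and 0.002 / 0.046 / 0.002 / 0.022 in control, in the order of the weights above.
- If interim and week-52 change correlate at ρ, removed participants lie d = ρ × 8.8 × E[Z | Z > z] from their arm mean. The complete-case shift in that arm is k·d/(65 − k).
- Largest case (300 lb, ρ = 0.8): with incentives, z = 2.62, E = 2.93, d = 20.6, shift 0.091. In control, z = 3.19, E = 3.46, d = 24.4, shift 0.017. Net 0.074 points.
- Across all four weights and ρ of 0.6 to 0.8, the net shift is 0.005 to 0.074 points, toward the null.

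**Serious adverse event or disordered eating.** Assume k = 1 to 3 removals, all from one arm, each d = 5 to 10 points from the arm mean in the same direction.

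- Complete case, k·d/(65 − k): 1 × 5/64 = 0.08; 2 × 10/63 = 0.32; 3 × 10/62 = 0.48.
- If imputation from interim BMI recovers a share ρ² of d, the residual shift is k·d·(1 − ρ²)/65. This runs from 1 × 5 × 0.36/65 = 0.03 (ρ = 0.8) to 3 × 10 × 0.64/65 = 0.30 (ρ = 0.6).

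**Against the precision of the trial.** At 20% attrition there are 65 × 0.8 = 52 per arm, and SE = 7.04 × √(2/52) = 1.38. Power for 5 points is Φ(5/1.38 − 1.96) = 95.2%.

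| Shift | In SE | 95% CI coverage | Power if the effect shrinks | Power if it grows |
|---|---|---|---|---|
| 0.48 (complete case) | 0.35 | 93.6% | 90.5% | 97.8% |
| 0.30 (after imputation) | 0.22 | 94.5% | 92.6% | 97.0% |

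Coverage is Φ(1.96 − b) − Φ(−1.96 − b), where b is the shift in SE units.

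**The case against.** The strongest reply is that this is an ambiguity, not an error. Sections 4.3.1 and 4.3.2 carry headings about withdrawn participants in general, 8.5 speaks of withdrawal too, and nothing forbids measuring a removed participant. It is true that loss of the week-52 value is inferred from removal rather than stated. It is nonetheless the natural reading, and no text provides for the measurement.

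Several points about size stand. The weight trigger contributes almost nothing. The assumption of one to three removals, all in one arm and in one direction, has no basis in the documents. Screening excludes known eating disorders and purging, and removal for disordered eating needs confirmation at interview. BMI is measured at six post-baseline visits, so imputation would often have interim values to use, and the complete-case worst case overstates what the planned analysis would show. A few removals also fit inside the 20% attrition allowance. Imputation lessens the harm but does not replace a value that could have been obtained, and 7.4 does not single these removals out.

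Safety is the other serious argument. These are minors on a 1,200 kcal regimen, and repeated weighing may be wrong for a teenager with disordered eating. That stands as a limit on the fix: some values will stay missing. It does not justify ending assessment for everyone removed. Timing also counts: this is Version 12, dated April 2022, so new wording helps only participants still in follow-up.

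**Conclusion.** The concern holds as a low-priority point. The removal rules in 8.5 and 11.4 leave the primary outcome uncollected for members of the intent-to-treat population, contrary to the aim of 4.3.1. The likely effect on the primary result is small. For the weight trigger, the bias is toward the null and could not create a false benefit. For the other two triggers the direction is unknown, and even the worst case considered is about a third of a standard error before imputation. These sizes rest on assumed removal rates, deviations, starting weights and correlations, and on the visit-to-visit reading of 11.4. More removals, or larger deviations concentrated in one arm, would give a larger shift. The case for change is that it costs little and serves the plan's own intent-to-treat purpose.

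**What to change.** Keep every trigger and the specialist referral. Reword 8.5 and 11.4 so that a trigger ends study meals and incentive payments. Week-26 and week-52 BMI and the safety assessments (adverse events, EDE-Q) would continue with consent and assent, where the medical safety lead judges this appropriate. Extend 4.3.1 and 4.3.2 to name investigator-initiated removals.

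The cost is protocol and consent wording, plus a few already scheduled visits for removed participants who agree. Sample size, alpha and Table 2 do not change.
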